Improving the effectiveness of orally dosed emergency contraceptives in women of varying weights/BMIs

PI: [name] [name], Dept. OB/GYN

Funding: Investigator initiated, National Institutes of Health

Specific Aim:

1. To determine if dose escalation for emergency contraception containing levonorgestrel results in improved pharmacodynamics outcomes for obese women.
2. To compare the pharmacokinetic parameters and pharmacodynamic profile of emergency contraception containing ulipristal acetate between obese and normal BMI women, and to determine if dose escalation improves how well it works in obese women.

Background

Emergency contraception (EC) provides a woman with an additional line of defense against unintended pregnancy following an act of unprotected intercourse. Orally-dosed EC [levonorgestrel (LNG) or ulipristal acetate (UPA)] works by blocking ovulation and reduces the risk of pregnancy for a single act of unprotected intercourse by up to 90% [1–3]. Unfortunately as the majority of U.S. women are either overweight or obese, LNG-based EC has diminished or no efficacy, the equivalent of taking a placebo pill [4–6]. Prevention and planning of pregnancies is critical as obese pregnant women are at higher risk of pregnancy complications endangering their own health and the development and post-natal health outcomes of the fetus [7]. Prior research from our group and others has proven that obesity adversely impacts the pharmacokinetics (PK) of contraceptive steroid hormones in combined (estrogen and progestin) oral contraceptive pill users [8,9]. In particular, drug half-life and clearance are affected. These changes in turn, cause a lower maximum concentration (Cmax) and a time delay in achieving Cmax and steady state [8–11]. This prior work provides insight into a possible mechanism for EC failure in obese users. As a single-dose therapy, EC is reliant on achieving a rapid peak level at a critical time point prior to the LH surge [12,13]. The PK profile following oral administration of LNG-EC is similar to that of LNG-based oral contraceptives, just a magnitude higher due to differences in the dosage [14]. We suspected that a critical level of the drug sufficient to block the LH surge is not being achieved in obese EC users. To test this, we performed preliminary studies and demonstrated that Cmax levels following oral administration of LNG-based EC are 50% lower in women of obese relative to normal body mass index (BMI) (15).

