We also tested an alternative dosing strategy in an effort to counteract these PK changes and demonstrated that obese women taking double the approved LNG EC dose normalized the PK profile to that of normal BMI women. Although a “take two” strategy could be rapidly implemented into clinical practice, we have no data on the resulting end-organ effects. Further studies are needed to document if PK normalization results in improved pharmacodynamic (PD) outcomes. Another alternative treatment strategy is to use a UPA-based EC instead. UPA is slightly more effective than LNG-based EC as it has a longer window of action (e.g. effective until LH peak vs. LH rise) [2]. However, published data demonstrate a possible decline in efficacy for obese women [4]. Detailed PK and PD studies for UPA have yet to have been performed in obese women but unpublished data from a colleague at Columbia University also demonstrated PK differences (*personal communication 4-2016*).

The overall goal of this research is to improve EC effectiveness and quality of clinical care for obese women. We hypothesize that increasing the dose of LNG- and UPA-based EC will normalize PK (specifically the time needed to reach a therapeutic drug level) and PD outcomes (follicle rupture) in obese women who weigh 80kg or greater. In this application we propose to expand our model for LNG- to UPA-based EC, assess the pharmacodynamic outcomes of these alternative dosing regimens (“take two”) in obese women and to assess the safety and acceptability of these regimens in this population.

Methods:

Study design: This is a 2-part study: Part 1 will be focused on LNG-EC and Part 2 will be focused on UPA-EC. Eligible women can take part in both aspects of the study and in no particular order. If they do choose to enroll

in both aspects of the study, then the screening visit does not need to be repeated unless it has been greater than 12 months since the original screening visit.

Part 1 LNG-EC is a randomized control trial. Part 2 UPA-EC is a randomized cross-over study with an additional non-randomized control arm.

This study will be conducted at Oregon Health & Science University (OHSU) in Portland, OR and a subcontract site, Eastern Virginia Medical School (EVMS) in Norfolk, Virginia. EVMS will be overseen by their own IRB.

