Rationale: Dose escalation is a commonly used strategy in pharmacotherapeutics [16]. We have already tested this strategy in our preliminary studies and demonstrated that we can normalize the LNG peak level in obese women by doubling the dose. It remains unknown if this improved drug level will translate into better end-organ suppression. However, we have had prior success with improved end organ suppression with dose escalation in our studies of oral contraceptives in obese women [11] thus we have confidence in this strategy for EC. The findings of our proposed studies, whether positive or negative, will provide critical information as we will have either proven or disproven if this potential solution works.

Part 1 LNG-EC:

The study flow for Part 1 is depicted in the graphic below. Part 1 will be performed as an open-label randomized control trial. Randomization will occur in a 1:1 fashion utilizing a computer generated random

permuted block randomization scheme with block size 4, 6 and 8.

Demographic information will be obtained including but not limited to race, ethnicity, parity, and prior contraceptive use. After

confirmation of ovulation via an elevated P4 of 3ng/mL or greater in the screening cycle.

Subjects will be randomized to treatment group [LNG-EC 1.5 mg (ECx1) or LNG-EC 3mg (ECx2)] and undergo a treatment cycle.

During the treatment cycle, subjects will undergo every other day visits starting on cycle day 6-8 followed by daily visits for up to 7 days once a dominant follicle measuring 15mm or greater in one diameter is visualized (see procedure flow below). Daily visits will cease prior to 7 days if evidence of follicle rupture (disappearance of or greater than 50% reduction in size of the dominant follicle) occurs. At each visit, subjects will undergo blood sampling via a single venipuncture for P4, E2 and LH levels and high-resolution transvaginal ultrasonography (TUS) (GE Ultrasound OR, 9900 Innovation, Voluson eBT11) to monitor follicular development and evidence of ovulation.

During the treatment cycle, study medication will be dosed on the day a ≥ 15 mm follicle is visualized. Women will be randomized to either LNG ECx1 (1.5mg LNG) or LNG ECx2 (3mg LNG). Study medications will be given by study staff and ingestion will be directly observed. Prior to ingesting study medication, women will undergo urine pregnancy testing to confirm non-pregnant status.

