Study end will be at the onset of menses at the end of the treatment cycle (defined as two consecutive days of spotting/bleeding). We estimate up to 12 visits in the treatment cycles depending if delay in ovulation occurs. Subjects will have the option to undergo a washout cycle and participate in the studies detailed in Part 2; if they chose to do so, they will not have to undergo another screening visit or control cycle.

Procedure flow:

	Visit 0 (Screening Visit)	Treatment Cycle Starting Cycle 1 day 6-8
Consent, Screening tests and medical history	X	
blood draws	X	X
ultrasound		X
Study Medication & urine pregnancy test		X*
Total time	2 hour	30 min/visit

*Visit number study medication will be taken depends on ultrasound findings.

Data Analysis & Sample Size: All analyses will be performed on an intention-to-treat (ITT) basis. To demonstrate equality between treatment arms at baseline, we will compare participant demographics using two sample t-test or chi-square test, and descriptive statistics such as mean, median and percentages within each group will be reported. **The primary outcome analysis will compare the proportion of women with no follicular rupture (yes/no) between the treatment groups using a Chi-square test.** As mentioned previously, follicle rupture will be defined as the disappearance of or $>50\%$ reduction of size of the leading follicle [2,17].

Confirmation of the timing of ovulation will be supported by LH, P4, and E2 levels. If necessary, we will address any unanticipated imbalances between the treatment groups after randomization by adjusting for these confounders in analysis using a logistic regression. Descriptive statistics will be utilized to report LH and P levels [mean (standard deviation)], follicular diameter [median (range)], and cycle day [median (range)] on the day of EC ingestion during the treatment cycle within each group. Additionally, the proportion of inhibition of follicular rupture by LH status (no surge, start of LH surge, or after LH peak) [2,17] for each cycle will be compared between treatment groups using fisher's exact test. Mean LH, P4, and E2 levels over time will be plotted by treatment group. Time from treatment intake to follicular rupture will be assessed by a survival

analysis using Kaplan-Meier curve and log-rank test. All statistical analyses will be performed with the SAS version 9.4 (Cary, NC, USA).

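### Does the open-ended 'if necessary' covariate adjustment in Part 1 undermine the primary comparison of LNG doses?

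*Combined protocol and SAP*

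**What the plan says.** The Part 1 Data Analysis & Sample Size section states that the "primary outcome analysis will compare the proportion of women with no follicular rupture (yes/no) between the treatment groups using a Chi-square test". Analysis is by intention to treat. Baseline demographics are compared by t-test or chi-square test. The adjustment sentence follows: "If necessary, we will address any unanticipated imbalances between the treatment groups after randomization by adjusting for these confounders", by logistic regression.

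LH is used in the same section. The plan compares between arms "the proportion of inhibition of follicular rupture by LH status (no surge, start of LH surge, or after LH peak" (three classes, Fisher's exact test), and it describes LH by arm on the day of ingestion.

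The design facts that bear on this are in Part 1 LNG-EC:
- "Part 1 will be performed as an open-label randomized control trial".
- "study medication will be dosed on the day a ≥ 15 mm follicle is visualized".
- "At each visit, subjects will undergo blood sampling via a single venipuncture for P4, E2 and LH levels".

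The Background explains why LH matters: "EC is reliant on achieving a rapid peak level at a critical time point prior to the LH surge", and UPA is credited with a "longer window of action (e.g. effective until LH peak vs. LH rise".

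**The concern.** Three things are missing from the adjustment sentence: which covariates, what degree of imbalance triggers it, and whether the adjusted result supports or displaces the chi-square. The baseline tests on demographics are the nearest thing to a trigger, but they have no cut-off and are not tied to the adjustment. Treatment is open-label, and the investigator reviews the data in depth when Aim 1 is complete (Data and safety monitoring section). A choice between an adjusted and an unadjusted result could therefore be made after both are known, and choosing the more favourable one would raise the false-positive rate.

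The plan's own rationale also points to one covariate. LNG is expected to act before the LH surge, but dosing follows follicle size, so women may differ in LH status when dosed. The plan tabulates inhibition by LH class but gives no single dose effect that allows for LH. It is natural to ask whether a fixed LH-stratified test should replace the loose sentence.

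**Working it through.** **1. The plan's sample size.** Inputs from Part 1 Data Analysis & Sample Size: 90% normal ovulation on ECx1 (10% inhibition), a 30-point difference (so 40% on ECx2), two-sided 5%, 80% power, 62 women (31 per arm).

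With the pooled-variance formula and a mean rate of 25%:

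n per arm = [1.960·√(2·0.25·0.75) + 0.842·√(0.10·0.90 + 0.40·0.60)]² / 0.30² = 31.5

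This rounds up to 32 per arm, or 64 in all, two more than the plan's 62. At 31 per arm the normal-approximation power is 79.3%. The exact binomial power of the uncorrected chi-square is 81.3%, and 85.2% at 35 per arm. The stated figure holds. The Z test used for sizing and the chi-square used for analysis are the same test, since z² equals the Pearson statistic.

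**2. Validity of the primary test.** Full enumeration of two binomials with a common rate gives the exact size:

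| Common inhibition rate | 31 per arm | 35 per arm |
|---|---|---|
| 10% | 5.5% | 5.7% |
| 15% | 5.3% | 5.3% |
| 25% | 5.1% | 4.8% |
| 40% | 5.2% | 4.8% |
| 50% | 5.6% | 4.3% |

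The test runs slightly above 5% at the plan's control rate. That is acceptable. Fisher's exact test would have size 1.0-1.3% at 10% and power of 73% (31 per arm) or 78% (35 per arm).

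**3. What the open sentence could do.** The number of covariates is not in the documents, so these are assumptions. With k independent baseline tests at 5%, the chance that at least one flags is 1 - 0.95^k: 14% for k = 3, 23% for k = 5, 40% for k = 10. Take five covariates, a p<0.05 trigger, and an analyst who then stresses the better of the two results. Simulated type I error is 4.4-5.8%, close to the chi-square's own range. Higher figures need more than the plan contains. A standardised-difference trigger of 0.25 gives 6.1-7.0%. Free choice of the best among unadjusted, single-covariate and all-covariate models gives about 6-9% for three or five covariates at 35 per arm. If the adjusted result were always the one used once triggered, there is no inflation (3.9-5.1%).

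**4. What an LH-stratified test would add.** Setting: 31 per arm, two LH strata, Cochran-Mantel-Haenszel (CMH) v chi-square, 200,000 simulated trials. The share dosed after surge onset (10/20/30/40%) and the inhibition rates by stratum are assumptions.

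| Setting | Chi-square power | CMH power |
|---|---|---|
| Overall 10% v 40%, none inhibited after onset | 81/81/81/81% | 82/84/87/90% |
| 10% v 40% before onset only, none after | 75/69/62/54% | 76/71/65/58% |
| LH not prognostic, 10% v 40% | 81% throughout | 80% throughout |

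The largest gain, about 8 points, needs 40% dosed late and 0.40/0.60 = 67% inhibition before onset on ECx2. In the first two settings the average Mantel-Haenszel risk difference stays within 0.5 points of the crude one (30.4 v 30.0 points at a 20% late share), so the estimate hardly moves.

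**The case for a change.** The strongest case for a change is that the gap is real, the trial is open-label, and one dated paragraph would close it at almost no cost. LH is already drawn at each visit. The class-by-class Fisher comparison splits small arms: before onset, at 10% v 40%, its power is 66/59/55/46% for late shares of 10/20/30/40%, and it yields no pooled effect. If chance puts at least 15 points more late-dosed women in one arm, and there is no dose effect, the chi-square rejects 6.5-9.5% of the time when 25-40% are inhibited before onset.

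Part of this stands: the sentence lacks covariates, trigger and reporting role. The rest does not carry a change.

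- **Conditional error.** The 6.5-9.5% applies only to trials with that imbalance, at inhibition rates well above the plan's. With 10% inhibited before onset and none after it is 4.7-5.8%, and the overall rate is then only 9/8/7/6% (10% times the share dosed before onset). Averaged over randomisation the test keeps the size shown above.
- **Mismatch.** The only baseline tests between arms are on demographics. Stratifying by LH does nothing for weight, BMI or site.
- **New difficulties.** LH status at dosing is measured after randomisation. The Part 1 LNG-EC section places only the urine pregnancy test explicitly before ingestion, so the draw order would need confirming. Women without a dosing-visit LH value would need a rule, and so would the LH cut-off. With 20% misclassification of LH, the change in power in the two settings with no inhibition after onset is only -0.6 to +2.5 points.
- **Investigator review.** It takes place on completion of Aim 1 and is described under data and safety monitoring. It gives no licence to change the primary analysis.

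**Conclusion.** The concern does not call for a change. Followed as written, the plan gives a sound primary conclusion: an unadjusted chi-square named in advance, sized on the equivalent test, with 81.3% exact power at 31 per arm and exact size of 5.5% (31 per arm) or 5.7% (35 per arm) at a 10% control rate. No passage lets the logistic model take its place, so the missing detail touches only a supporting result. An analyst can fill it in the ordinary way, by reporting any adjusted odds ratio as secondary beside the chi-square and stating which covariates were used and why.

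The error-inflation figures depend on an assumed number of covariates and on selective emphasis that the plan does not permit. The power gains from LH stratification depend on assumed late-dosing shares and stratum rates, and run from about -1 to +3 points outside the one favourable setting. An LH-stratified summary would be a reasonable exploratory extra if LH status came from samples confirmed as drawn before ingestion. Leaving it out is a fair choice, and the planned comparison by LH class already addresses the mechanism.

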We believe that the difference between groups will be large (50% or greater) given that LNG ECx1 in obese women appears to be equivalent to placebo (normal ovulation) as well as the large PK differences we found in our preliminary studies. However, we have chosen a more conservative difference (30%) in which to base our sample size calculations to ensure we have the ability to capture a range of differences. A sample size of 62 will achieve 80% power to detect a 30% difference in the proportion of cycles that demonstrate inhibition of follicular rupture (yes/no) using a two-sided Z test with a 5% significant level assuming 90% rate of normal time to ovulation in LNG ECx1 dose group. **We plan to screen up to 80 women to account for screen failures and enroll a total of 70 women to account for drop out.**

Part 2 UPA-EC, obese BMI and a weight of 176 lbs or more and normal BMI and a weight of less than 176 lbs, randomized cross-over trial.

Specific Aim: To compare the pharmacokinetic parameters and pharmacodynamic profile of emergency contraception containing ulipristal acetate between obese and normal BMI women, and to determine if dose escalation improves how well it works in obese women.

Hypothesis: The peak drug level of UPA-EC is lower in obese women than in normal BMI women which adversely impacts the therapeutic effect and dose escalation will improve drug efficacy for obese women.

[figure not shown]

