Rationale: Published data indicate a possible decline in the efficacy of UPA-EC for obese BMI women [4]. This lack of clarity is leading to concern among clinicians that no orally-dosed EC agent is effective in women of higher weight or BMI. UPA is metabolized differently than LNG. LNG is highly protein bound and our studies have established that obesity adversely impacts LNG clearance, half-life and specific to LNG EC, peak levels [9,10]. UPA, unlike LNG, binds distinctly to alpha-acid glycoproteins and high density lipoproteins. Obesity is known to alter serum/plasma profiles of both drug-binding proteins: Alpha-acid glycoprotein levels are usually doubled [19], and dyslipidemia of obesity is often characterized by low HDL [20]. The net effect of obesity induced changes in UPA binding proteins is unknown yet, however could be speculated as high degree of binding resulting in reduced concentration of pharmacologically relevant drug. Detailed PK and PD studies for UPA in an obese cohort have not been performed. We propose to perform these studies as a randomized cross-over study. This design will reduce variability in the PK data as obese subjects will act as their own controls for comparisons between ECx1 and ECx2. **We have also chosen to include a small control group of normal BMI subjects in order to verify the accuracy of our PK findings.**

Part 2 UPA-EC:

The study flow for Part 2 is depicted in the graphic to the right. Part 2 will be performed as an open-label randomized cross-over study. Randomization will occur in a 1:1 fashion utilizing a computer generated random permuted block randomization scheme with block size 4, 6 and 8.

Demographic information will be obtained including but not limited to race, ethnicity, parity, and prior contraceptive use. If subjects did not participate in Part 1, they will undergo confirmation of ovulation via an elevated P4 of 3ng/mL or greater in the screening cycle. =.

During the treatment cycles, subjects will undergo every other day visits starting on cycle day 6-8 followed by daily visits for up to 7 days once a dominant follicle measuring 15mm or greater in one diameter is visualized. Daily visits will cease if evidence of follicle rupture occurs, either disappearance of or greater than 50% reduction in size of the dominant follicle. At each visit, subjects will undergo blood sampling via a single venipuncture for P4, E2 and LH levels and transvaginal ultrasonography

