(TUS). The TUS will be performed using a high-resolution transvaginal ultrasonography (GE Ultrasound OR, 9900 Innovation, Voluson eBT11) to monitor follicular development and evidence of ovulation. During the treatment cycles, study medication will be dosed on the day a 15 mm follicle is visualized. Both the normal and obese BMI groups will undergo treatment cycle 1 and receive a standard dose of UPA EC (30mg) or ECx1. After at least one washout cycle, only the obese group will complete treatment cycle 2 and receive a double dose of UPA EC (60mg). Study medications will be given by study staff and ingestion will be directly observed. Prior to ingesting study medication in each treatment cycle, women will undergo urine pregnancy testing. Study end will be at the onset of menses at the end of the treatment cycle (defined as two consecutive days of spotting/bleeding). We estimate that approximately up to 12 visits in the treatment cycles depending if delay in ovulation occurs.

During each treatment cycle, PK parameters will be obtained via serum samples through an indwelling catheter. IV placement in obese women can be challenging. We will enlist the assistance of OHSU's NIH funded CTSA nursing staff or IV therapy, if necessary, to place IVs in our obese cohort in order to ensure the least traumatic process for our subjects. We plan to obtain samples at 0.5, 1, 1.5, 2, 3, 4, 24, 48, 72, 96, and 120 hours for our normal controls in treatment cycle 1 and a subset of the obese cohort (n=30) in both treatment cycle 1 and 2. The IV will be left in place for the closely spaced samples and then single samples via phlebotomy will be obtained on the samples timed at 24 hours and later. This extended sampling scheme will allow us to determine a more accurate area under the curve by having observed rather than estimated values. Furthermore a prolonged sampling scheme will enable estimation of additional PK parameters that can lead to mechanistic insights.

Of note, Eastern Virginia Medical School will not be recruiting or enrolling participants for the Part 2 – UPA Normal BMI cohort as enrollment of the 12 participants for this group is complete.

Procedure flow for obese BMI study groups

	Screening Visit (1 visit)	Treatment Cycle 1 Starting Cycle day 6-8 (up to 12 visits)	Washout Cycle 2 (no visits)	Treatment Cycle 3 Starting Cycle day 6-8 (up to 12 visits)
Consent, Screening tests and medical history	X			
Phone or email contact			X	
Blood draws	X	X		X

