Ultrasound		X		X
Study Medication & urine pregnancy test		X*		X*
Longer series of blood draws (over 5 hours)		X**		X**
Total time	2 hours	30 min/visit for all but 2 visit which will be 2 or 5 hours		30 min/visit for all but 2 visit which will be 2 or 5 hours

*Visit number study medication will be taken depends on ultrasound findings.

**The study visit on the day the study medication is taken will last 2 hours (curtailed PK) or 5 hours (full PK)

Procedure flow for Normal BMI control group

	Screening Visit (1 visit)	Treatment Cycle 1 Starting Cycle day 6-8 (up to 12 visits)
Consent, Screening tests and medical history	X	
blood draws	X	X
ultrasound		X
Study Medication & urine pregnancy test		X*
Longer series of blood draws (over 5 hours)		X**
Total time	2 hour	30 min/visit for all but 1 visit which will be 5 hours

*Visit number study medication will be taken depends on ultrasound findings.

**The study visit on the day the study medication is taken will last 5 hours

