PK parameter analysis. UPA PK parameters will be generated by noncompartmental methods using WinNonLin (Pharsight, Mountain View, CA). Cmax and time to maximum Cmax will be observed values. Area under the curve (AUC) will be calculated from Time 0 to 120hr (AUC0-120) using the linear trapezoidal rule and then extrapolated to infinity which provide a more accurate calculation of drug clearance (Rowland 1980). Drug half-life (t1/2), oral clearance (CL), and volume of distribution (VD) will be generated using standard pharmacokinetic calculations ($t_{1/2} = 0.693/\lambda_z$ where λ_z is the terminal elimination rate constant; $CL = dose/AUC_{0-\infty}$; $VD = CL/\lambda_z$). Descriptive statistics will be generated for each parameter [mean (standard deviation)], concentration-time curves will be generated for all of the doses and their respective BMI groups. Depending on the normality of the data, parametric or nonparametric testing will be performed for each parameter between the normal and obese BMI ECx1 groups and paired statistics will be utilized to compare obese BMI ECx1 and ECx2.

We also plan to perform analyses to compare PD outcomes in obese users ingesting LNG and UPA, ECx1 and ECx2. UPA and LNG are the only two orally-dosed EC agents available on the market. A logical sub analysis is the comparison of the different dosing strategies to help guide future studies or even clinical management of orally-dosed EC in obese women if dose escalation appears effective. We will utilize the data collected in Aim 1 and 2. The proportion of women with a delay in follicular rupture (yes/no) in 4 different treatment regimens obtained in the trial in aim1 and 2 will be compared and test if there's significant difference

between LNG ECx2 and UPA LNG ECx2 using Chi-square test. Due to exploratory purpose of these analyses, the analysis will be descriptive but given the projected sample size (35 per group in Part 1 and 80 per group in Part 2) we will achieve more than 80% power with 5% of significance level to detect 23% difference in delay in follicular rupture. In addition, one of the secondary outcomes of time from treatment intake to follicular rupture will be compared among treatment groups using survival analysis.

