A sample size of 73 will achieve 80% power to detect a 20% difference in the proportion of cycles that demonstrate at a delay in follicular rupture (yes/no) using a two-sided McNemar test with a Bonferroni-adjusted 2.5% significant level. We estimate that 40 women will choose to participate in Aim 2 after completing Aim 1 studies and plan to screen an additional 58 women to account for screen failures for a total enrollment of 80 women to account for drop out. We believe that the difference between groups will likely be smaller given the clinical information (50% or less). We have chosen a difference of 20% in which to base our sample size calculations. We have consciously chosen not to enroll an adequately sized normal BMI group to detect the same amount of difference (20%) given that there are published PK/PD standards. We are utilizing this group to verify the accuracy of our findings under our environment, the targeted 10 total number of subjects (after 12 screening) in the control arm would achieve the 80% power to detect 47% difference in follicular rupture given the 73 of women taking UPA ECx1 using two-sided Z test with 2.5% significance level. The total number of subjects in the control arm was chosen as a convenience sample but this number of subjects should supply us with an adequate amount of data to ensure that our PK/PD results are similar to published values in a normal BMI cohort.

Protection of human subjects:

1. Risks to Subjects

Human Subjects Involvement and Characteristics

Reproductive-aged (18-35 year old), ovulatory, healthy women with a normal or obese BMI with no contraindications to the study medications and not at risk for or seeking pregnancy will constitute the target population for this study.

All enrollment and clinical evaluations will be performed at OHSU in Portland, Oregon. Serum samples will be prepared at OHSU and analyzed at the ONPRC Endocrine Core Laboratory under the direction of [name]. De-identified pharmacokinetic data will be analyzed by our consulting pharmacokinetic specialist, [name].

Sources of Materials

The sources of research material for the clinical portion of this proposal will be new specimens obtained purely for this research protocol. The study investigators and/or research assistants/nurses will perform all study procedures.

Potential Risks

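### The linear trapezoidal rule on a schedule with no sample between 4 and 24 h would overstate UPA AUC, and so understate CL and VD, if the drug peaks by about 3 h and declines convexly; the size depends on kinetics the plan does not give, and the remedy is cheap

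*Combined protocol and SAP*

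**What the plan says.** The Part 2 UPA-EC section sets the schedule: "We plan to obtain samples at 0.5, 1, 1.5, 2, 3, 4, 24, 48, 72, 96, and 120 hours for our normal controls", and the same times for a subset of 30 obese women in both treatment cycles. A catheter serves the early samples; after that, "single samples via phlebotomy will be obtained on the samples timed at 24 hours and later". For the control group, the procedure-flow footnote reads: "The study visit on the day the study medication is taken will last 5 hours". Nothing is therefore drawn between 4 and 24 h.

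The PK parameter analysis section then states that AUC is "calculated from Time 0 to 120hr (AUC0-120) using the linear trapezoidal rule and then extrapolated to infinity". CL is dose divided by AUC to infinity, and VD is CL divided by the terminal rate constant λz. It adds: "Cmax and time to maximum Cmax will be observed values". Each parameter is to be tested between normal-BMI and obese women on ECx1, and compared within obese women between ECx1 and ECx2.

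The Part 2 sample-size text describes the normal-BMI arm as a convenience sample that should give an "adequate amount of data to ensure that our PK/PD results are similar to published values in a normal BMI cohort". The PK part of the Part 2 hypothesis concerns the peak: "The peak drug level of UPA-EC is lower in obese women than in normal BMI women".

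**The concern.** On a convex falling curve, a straight line between two samples lies above the curve, and the excess grows with the gap relative to the half-life. Here one gap is 20 h and the four after it are 24 h each. AUC would be overstated, and because CL and VD have AUC in the denominator, both would be understated.

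The condition is an early peak. The documents do not state one, but the schedule presupposes it: six of the eleven samples fall within 4 h, the full-PK dosing visit ends at 5 h, and the peak is to be read directly from the samples. A peak inside the gap would weaken or reverse the bias.

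At stake are the absolute AUC, CL and VD values and their comparison with published normal-BMI values. These are supporting results.

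**Working it through.** The plan gives no AUC, half-life or Tmax for UPA, so there is no stated figure to reproduce. All kinetic values below are assumptions, shown as ranges.

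**Inputs from the plan.** Sampling times 0.5, 1, 1.5, 2, 3, 4, 24, 48, 72, 96 and 120 h; linear rule; extrapolation to infinity; CL = dose/AUC0-∞; VD = CL/λz.

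**Assumed.** C(0) = 0; λz from the last three points; tail = C(120)/λz; exact integrals as truth.

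**Step 1, one-phase decline.** C(t) ∝ ka/(ka − k) × (e^(−kt) − e^(−ka·t)), with ka = 2/h and k = 0.693/half-life. Example at a 24 h half-life:

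- C(4) = 0.9036 and C(24) = 0.5073, so the linear area over 4–24 h is 20 × (0.9036 + 0.5073)/2 = 14.11.
- The exact area is 13.73 and the true AUC0-∞ is 24/0.693 = 34.62.
- The gap adds (14.11 − 13.73)/34.62 = about 1.09 points. The later 24 h intervals add 1.89, and the rising part takes off about 0.13, giving +2.85%.

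| Half-life (h) | AUC0-∞ error, linear | 4–24 h share of AUC0-120 error |
|---|---|---|
| 48 | +0.6% | 25% |
| 32 | +1.6% | 32% |
| 24 | +2.85% | 38% |
| 18 | +4.9% | 47% |
| 12 | +9.8% | 62% |
| 6 | +27.9% | 88% |

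CL and VD change by 1/(1 + error) − 1: −2.8% at 24 h, −8.9% at 12 h, −21.8% at 6 h. Linear-up/log-down is within 0.6% in all six rows.

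**Step 2, two-phase decline.** C(t) = f·e^(−at) + (1 − f)·e^(−bt) − e^(−ka·t), with ka = 2/h, fast half-life 1.5, 3 or 5 h, fast fraction f of 0.5, 0.7 or 0.9, and terminal half-life 24, 32 or 48 h: 27 cases.

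- f = 0.5 or 0.7: +2.3% to +14.7%.
- f = 0.9: +13.5% to +31.6%.
- Median of all 27: +9.9%. The 4–24 h gap supplies 74% to 99% of the AUC0-120 error.
- CL and VD: 1/1.0233 − 1 = −2.3%, to 1/1.3157 − 1 = −24.0%.
- Linear-up/log-down: +1.4% to +13.6%, closer to the truth in 27 of 27.

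**Step 3, slower absorption.** A wider grid of 297 profiles (ka 0.3 to 4/h), split by the observed time of the highest sample:

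| Highest sample | Linear error | Log-down error | Log-down closer |
|---|---|---|---|
| 3 h or earlier | +0.6% to +35.5% | −3.6% to +18.4% | 207 of 207 |
| 4 h | −3.3% to +19.5% | −13.6% to +3.8% | 54 of 89 |
| 24 h | – | – | 0 of 1 |

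A reversal: at ka = 0.5/h and a 24 h half-life, linear gives −0.25% and log-down −2.76%.

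**Step 4, against sampling error.** Assume a CV of 30% to 50%; the log-scale SD is s = √ln(1 + CV²), i.e. 0.294 to 0.472. Take 10 to 12 control women, since the plan targets 10 and reports 12 enrolled.

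- 95% CI factor for one geometric mean, exp(t·s/√n): 1.23 (n = 10) and 1.21 (n = 12) at CV 30%; 1.40 and 1.35 at CV 50%.
- Only 4 of the 27 two-phase errors exceed a factor of 1.21, all at f = 0.9; none reaches 1.35.
- False obese versus normal ratio when only the half-life differs (24 h against 32 or 48 h): 1.012 to 1.022 one-phase, 1.019 to 1.093 two-phase. The ratio detectable with 80% power against 30 obese women, exp(2.80·s·√(1/n + 1/30)), is 1.32 to 1.62.

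**The case against.** The linear rule is a recognised noncompartmental option, it is prespecified, and it applies alike to every group. Nothing in the documents shows a short half-life or a large fast phase, and with slow one-phase decline the error is too small to matter. All two-phase errors above 15% need a fast fraction of 0.9. The replacement rule does not fill the gap, and it can do worse when the peak is late. The published values may share the linear rule, in which case changing it would harm comparability. Most of this stands, and it limits the point to a cheap improvement. What remains is that log-down was closer in every profile run with an observed peak at 3 h or earlier, which is the pattern the schedule is built for.

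A reader might infer three stronger things that the documents do not support:

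- **That the PK comparisons are compromised.** A proportional error cancels between ECx1 and ECx2 under dose proportionality. Between BMI groups only a difference in error remains, and a difference in UPA kinetics is not established: the Part 2 rationale says "The net effect of obesity induced changes in UPA binding proteins is unknown yet".
- **That the control arm will falsely disagree with published values.** Most of the assumed errors lie inside that arm's own confidence interval. The plan sets no numerical criterion for agreement, and the rule and schedule behind the published values are not given.
- **That the 4–24 h gap is always the cause.** In the under-3% cases most of the error comes from the later 24 h intervals.

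**Conclusion.** The point holds conditionally and is minor. Given a peak by about 3 h and convex decline, the planned rule overstates AUC and understates CL and VD. How much cannot be settled from the documents; the error may be negligible under slow one-phase decline or substantial with a short half-life or a dominant fast phase. The VD figure also assumes that λz is estimated well.

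Only the absolute AUC, CL and VD values are exposed. The primary outcome does not use them, nor do Cmax, Tmax or half-life. The error alone could push the control arm away from published values only in the extreme cases, and only if those values came from a different rule or schedule. That reading rests on the assumed CV of 30% to 50% and treats the published values as exact. Confidence is medium: the arithmetic is firm, the kinetics are not.

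**What to change.** In the PK parameter analysis section, replace the sentence on the linear rule with text to this effect:

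> AUC0-120 and AUC0-∞ will be calculated by the linear-up/log-down trapezoidal rule (linear while concentrations rise, logarithmic while they fall) in all groups and cycles. CL and VD from this AUC are the primary values. AUC, CL and VD by the linear rule will be reported as a sensitivity analysis. The number of profiles in each group whose highest observed concentration is at 4 h or later will be reported, and the AUC, CL and VD summaries will be repeated without them.

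The linear-rule results keep comparability with any published values that used that rule. The repeat summary shows whether late-peaking profiles, where neither rule is reliable, drive the result.

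**Cost.** One software setting and a few lines of text; no new samples or visits. This suits the control arm, whose enrolment the plan reports as complete.

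**Limits to state.** Log-down reduces two-phase error without removing it: about +1% to +14% remains in the main runs, up to +18% in the wider grid. It can also understate AUC when the true peak lies in the gap: for one-phase decline, by about 1% to 3% at half-lives of 24 h or more with ka 0.5 to 0.7/h, about 7% at 6 h with ka 0.5/h, and more with slower absorption.
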